5.5.2 Secondary Endpoint

The secondary efficacy endpoint is the proportion of subjects with clinical success on the Investigator's Global Assessment (IGA) at Week 12 (Visit 4/Day 84), where success is defined as an IGA score that is at least 2 grades less than the baseline assessment.

Equivalent Efficacy

The Test treatment will be considered to be therapeutically equivalent to the Reference treatment if the 90% Wald confidence interval with Yates' continuity correction on the difference in their success proportions is contained within the interval of -20% to +20%.

Superiority

The proportion of subjects with clinical success for each active treatment will be compared separately between each of the active treatments and the Vehicle using two-sided, $\alpha = 0.05$, continuity-corrected Z-tests.

Equivalence and superiority analyses will be conducted in both the PP and mITT populations.

5.5.3

A large rectangular area of the page is completely blacked out, indicating redacted content.

5.6 Safety Variables and Analyses

Duration of Treatment and Medication Compliance

Number of applications, days of exposure, and compliance rate will be summarized by treatment group using descriptive statistics. For each subject, the overall duration of treatment (days) will be calculated using the following formula:

$$\text{(Date of last application of study medication)} - \text{(Date of first application of study medication)} + 1.$$

Medication compliance rate (%) will be calculated for each subject as follows:

$$\text{(Total number of applications used)} / \text{(Expected number of applications)} *100\%.$$

Adverse Events

Adverse events (AEs) will be coded in MedDRA, version 15.1. Treatment-Emergent Adverse Event (TEAE) is defined as any AE occurs on or after applying the first dose of study drug. Number and percent of subjects reporting TEAEs will be tabulated by treatment group. Summaries will be presented by body system and preferred term for the ITT population. Similar tables will be presented by severity and relationship to study drug. TEAEs reported by more than 5% subjects for any treatment group will also be summarized. In summaries of incidence rates (frequencies and percentages), severity and relationship to study drug, subjects who report more than one event that are mapped to the same preferred term will be counted only once under the strongest severity and relationship, accordingly. The difference between Test and Reference treatments with regard to the severity and frequency of their dermatological adverse events will be statistically evaluated. Fisher's exact test will be used to compare the proportions of subjects of the two active treatment groups who report any TEAE.

Treatment-Emergent Serious Adverse Events (TESAEs) and TEAEs that led to treatment interruption or discontinuation will be presented in [data listings](#).

Concomitant Medications

Concomitant medications will be coded using the WHO Drug Dictionary, version September, 2014, and will be presented in [data listings](#).

Application Site Reactions

Frequency and distribution of application site reactions of erythema, dryness, scaling/peeling, burning/stinging, erosion, edema, pain and itching will be summarized and compared descriptively by visit.

Safety comparisons will be performed only for the ITT population.

6 Appendices

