7.2 Definitions

An adverse event (AE) is defined as any untoward medical occurrence in a subject administered a medicinal product and which does not necessarily have to have a causal relationship with this treatment. An adverse event can therefore be any unfavorable and unintended sign (for example, an abnormal laboratory finding), symptom, or disease temporally associated with the use of a medicinal product, whether or not considered related to this medicinal product.

A serious adverse event (SAE) is an adverse event that results in any of the following outcomes:

- death
- life-threatening event (i.e., the subject was, in the opinion of the investigator, at immediate risk of death from the event as it occurred. It does not include an event that, had it occurred in a more severe form, might have caused death)
- requires in-subject hospitalization or prolongs hospitalization
- a persistent or significant disability/incapacity or substantial disruption of the ability to conduct normal life functions
- congenital anomaly/birth defect
- Other adverse events that may be considered serious based upon appropriate medical judgment, may jeopardize the subject and may require medical or surgical intervention to prevent one of the outcomes listed above.,

Immediately Reportable Adverse Events (IRAE): Any serious AE or any AE that necessitates discontinuation of study medication, including pregnancy.

Protocol No: PRG-NY-15-003

Unexpected Adverse Event: An unexpected event is any adverse drug experience, the specificity or severity of which is not consistent with the current approved product labeling (package insert) for the study medication, the Investigator's Brochure, or as described in the clinical protocol and consent materials.

Intensity of Adverse Events: The maximum intensity of an AE during a day should be recorded on the CRF. If the intensity of an AE changes over a number of days, then separate entries should be made having distinct onset dates for the changes in severity.

Mild - AEs are usually transient, requiring no special treatment, and do not interfere with subject's daily activities.

Moderate - AEs typically introduce a low level of inconvenience or concern to the subject and may interfere with daily activities, but are usually ameliorated by simple therapeutic measures.

Severe - AEs interrupt a subject's usual daily activity and traditionally require systemic drug therapy or other treatment.

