7.3 Eliciting and Reporting of Adverse Events

The investigator will periodically assess subjects for the occurrence of adverse events. [REDACTED]

[REDACTED] All adverse events (as defined in Section 7.2), either observed by the Investigator or one of his/her medical collaborators, or reported by the participant spontaneously, or in response to direct questioning, will be reported and documented in the source and the study reporting forms. When reporting an adverse event, the Investigator must assign a severity grade to each event and declare an opinion on the relatedness of the event to the study medication or procedure. Serious or unexpected adverse events must be reported to Perrigo **within 24 hours** of when the Investigator first learns of the occurrence of the event.

Adverse events will be documented in the source document and recorded in a timely manner on case report forms. Adverse events (e.g., worsening of acne*) that are identified at the last assessment visit (or the early termination visit) must be recorded on the AE case report form (CRF) with the status of the AE noted.

* Worsening of the subject's acne may be expected from application of the study medication. This will only be reported as an adverse event if a subject is discontinued from the study or an alternate treatment is required.

Adverse event reporting begins from the signing of informed consent/assent. Adverse events should be followed until resolved or 30 days after the final study treatment. In any case, serious adverse events that are not resolved or considered to be chronic within 30 days of the final study treatment must be followed by the investigator until they become resolved or are considered to be chronic (stabilized for at least 30 days). All events that are ongoing at this time will be recorded as ongoing on the CRF.

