9. CONSENT/ASSENT CONSIDERATIONS AND PROCEDURES

It will be made clear to the subject that, for the purposes of the study, they are consenting only for topical application of medication or vehicle. Investigators may discuss the availability of the study and the possibility for entry with a potential subject without first obtaining consent/assent. However, informed consent/assent must be obtained and documented prior to initiation of any procedures that are performed solely for the purpose of determining eligibility for research, including withdrawal from current medication(s). When this is done in anticipation of, or in preparation for, the research, it is considered to be part of the research.

The study must be approved in writing by an appropriate IRB as defined by FDA regulations. A copy of the Letter of Approval from the IRB, which also contains specific identification of the documents approved, must be received by Perrigo, prior to study commencement.

Periodic status reports must be submitted to the IRB at least annually as required by the site's IRB, as well as notification of completion of the study and a final report within three months of study completion or termination. A copy of all reports submitted to the IRB must be sent to Perrigo.

The investigator(s) has both ethical and legal responsibility to ensure that each subject being considered for inclusion in this study is given a full explanation of the protocol. This shall be documented on a written informed consent/assent form, which shall be approved by the same Institutional Review Board (IRB) responsible for approval of this protocol. Each informed consent/assent form shall include the elements required by FDA regulations in 21 CFR Part 50. The investigator agrees to obtain approval from Perrigo of any written informed consent/assent form used in the study, preferably prior to submission to the IRB.

Once the appropriate essential information has been provided to the subject and fully explained by the investigators (or a qualified designee) and it is felt that the subject understands the implications of participating, the IRB-approved written informed consent/assent form shall be signed by the subject (or their parent/legally authorized representative) and the person obtaining consent/assent (investigator or designee). The subject shall be given a copy of the signed informed consent/assent form and the investigator shall keep the original on file.

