6.1 Handling of Missing or Incomplete Dates for Adverse Events and Concomitant Medications

Adverse Events

Handling of partial dates is only considered for the start date. An adverse event with a partial start date is considered treatment emergent if:

- only the day is missing and the start month/year is the same or after the month/year of the first dose
- the day and month are missing and the start year is the same or greater than the year of the first dose date
- the start date is completely missing

Concomitant Medications

Handling of partial dates is only considered for the stop date. A medication with a partial stop date is considered concomitant if:

- only the day is missing and the stop month/year is the same or after the month/year of the first dose
- the day and month are missing and the stop year is the same or greater than the year of the first dose date
- the stop date is completely missing or the medication is ongoing

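### SAP 6.1 classes an adverse event with a partial or missing start date as treatment-emergent even when its recorded stop date is before the first dose, which contradicts SAP 5.6

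*SAP*

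**What the plan says.** SAP 5.6 (Adverse Events) states that a TEAE "is defined as any AE occurs on or after applying the first dose of study drug". It sets no condition on severity relative to the pre-dose state and none on the stop date.

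SAP 6.1 begins its adverse-event rules with "Handling of partial dates is only considered for the start date". An event with an incomplete start date is then treatment-emergent in any of three situations. One is that "only the day is missing and the start month/year is the same or after the month/year of the first dose". Another makes the same comparison by calendar year when neither day nor month is known. The last is that no start date was recorded at all. No stop-date exception follows.

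Three protocol provisions bear on this. Section 2.2 has the end date of each adverse event recorded. Section 7.3 says "Adverse event reporting begins from the signing of informed consent/assent", so pre-dose events can enter the data. Section 7.2 says that when an event's intensity changes from day to day, "separate entries should be made having distinct onset dates for the changes in severity"; this is not limited to increases.

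The TEAE flag feeds the SAP 5.6 summaries by term, severity and relationship, and a Fisher's exact test of Test against Reference on the proportion of subjects with any TEAE.

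**The concern.** An event that has ended before the first dose cannot have emerged on treatment. SAP 5.6 excludes it; SAP 6.1, applied as written, includes it whenever the start date is incomplete in one of the listed ways. A programmer following 6.1 would set the flag against the SAP's own definition, and the conflict would have to be settled record by record.

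What is at stake is the content of the TEAE tables and the any-TEAE comparison. Protocol 8.1.5 uses a comparison of the proportions with any adverse event to judge whether Test and Reference are comparably safe. Pre-dose events are expected to be balanced by randomisation, so counting them raises both rates and narrows the relative contrast. That is the direction that favours a finding of no difference.

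**Working it through.** The documents give no figure for this point, so there is none to reproduce. The check is a comparison of the rules, followed by an assumed-value illustration of direction.

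**1. Partial dates.** Let T be the first-dose date. SAP 6.1 flags an event if:
- the day is missing and (year, month) of start ≥ (year, month) of T; or
- the day and month are missing and year of start ≥ year of T; or
- the start date is wholly missing.

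Under SAP 5.6 the event must occur on or after T. If stop < T, then start ≤ stop < T, and the event lies wholly before the first dose. Constructed records, with T assumed to be 15 June 2015:

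| Start | Stop | SAP 6.1 | SAP 5.6 | 6.1 with stop-date check |
|---|---|---|---|---|
| June 2015, day missing | 12 June 2015 | TEAE | not TEAE | not TEAE |
| 2015, day and month missing | 12 June 2015 | TEAE | not TEAE | not TEAE |
| wholly missing | 12 June 2015 | TEAE | not TEAE | not TEAE |
| May 2015, day missing | 30 May 2015 | not TEAE | not TEAE | not TEAE |

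The first three rows are the contradiction, one for each branch of 6.1.

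**2. Severity entries (complete dates).** With the same T, take an event that is moderate from 10 to 17 June and has a new mild entry with onset 18 June.
- If each entry counts as an AE, the mild entry is a TEAE under 5.6.
- If the AE is the underlying event, which began on 10 June, it is not.

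Now take an event that is mild before T and has a severe entry with onset 20 June.
- If each entry counts as an AE, the severe entry is a TEAE, as one would want.
- On a strict first-onset reading it is not.

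Neither reading, applied uniformly, excludes the decrease and keeps the increase. The SAP's rule of counting a subject once per preferred term removes duplicates among TEAEs but does not tie an entry to its pre-dose record.

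**3. When the problem can arise.** Adverse events are collected only from consent. A stop date before T therefore needs consent on an earlier date than T. If both fall on Day 1, no record of the kind in step 1 can exist.

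**4. Direction only.** Let p be the true any-TEAE proportion and m the share of otherwise TEAE-free subjects wrongly flagged in each arm. Then p' = p + (1 − p)m. All values here are assumed: p = 20% and 26%, m = 0 to 5%.
- m = 0 (same-day consent and dose): 20.0% and 26.0%, ratio 1.30.
- m = 1%: 0.20 + 0.80 × 0.01 = 20.8%; 0.26 + 0.74 × 0.01 = 26.7%; ratio 1.29.
- m = 5%: 0.20 + 0.80 × 0.05 = 24.0%; 0.26 + 0.74 × 0.05 = 29.7%; ratio 1.24.

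The documents support none of these inputs, and the visible schedule points towards the m = 0 end.

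**The case against.** The strongest reply is that the pre-dose window is nearly empty. The listed contacts are Baseline/Day 1, the Week 2 call and Weeks 4, 8 and 12, with no separate screening visit. Protocol 5.11 has the first application made at the site on Day 1. A gap between consent and dosing rests only on general wording in Protocol 9, which requires consent before medication is withdrawn for the study and mentions a screening phase, with no visible length. The partial-date problem also needs an unknown start together with a known stop inside that window. All of this stands. It limits the effect but does not reconcile 6.1 with 5.6.

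It is also fair to say that treating an unknown start as treatment-emergent is cautious and customary, and that 5.6 read alone already excludes an event known to have ended earlier. Both are right. The convention has no purpose, however, once the stop date has settled the question, and 6.1 does not say that 5.6 overrides it.

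A reader might go further and infer that the SAP plainly counts pre-dose events that merely lessen after Day 1. The documents do not establish that. SAP 5.6 speaks of an AE occurring, and Protocol 7.2 divides one AE into severity entries; a milder entry need not be a new AE. This is an ambiguity.

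A reader might also infer a material bias towards comparable safety. That is not supported either. The visible text gives any-TEAE no equivalence margin or pass/fail rule. The Fisher test sits beside tables by term, severity and relationship, the AE listings, and a further statistical evaluation of dermatological events. Application site reactions are scored separately at baseline and at each visit.

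**Conclusion.** The partial-date point holds on the text. SAP 6.1 and SAP 5.6 disagree about any event with an incomplete start date, of a kind that 6.1 flags, whose recorded stop date is before the first dose. The severity-entry point stands only as a request for clarification.

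The effect is probably very small and cannot be quantified from the documents. It arises only if consent precedes the first-dose date, and it is confined to the TEAE tables and the any-TEAE Fisher test. It does not touch efficacy.

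The conclusion assumes that no blacked-out text elsewhere holds a further rule. There are redactions in Protocol 7.3 and 8.1.5, but the adverse-event text of SAP 5.6 and SAP 6.1 shows none. The point is worth correcting because the correction is simple, not because the safety conclusion is in doubt.

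**What to change.** 1. In SAP 6.1, add that an AE whose recorded stop date is before the first-dose date is not treatment-emergent, whatever is missing from its start date. Where the stop date is itself partial, apply this only if the known part is enough to place it before the first dose. A stop date on the day of first dose would not exclude the event.
2. In SAP 5.6, as a clarification, state how the severity entries required by Protocol 7.2 are handled. For an AE that began before the first dose, an entry recording a decrease is not a new TEAE, and an entry recording an increase after the first dose is. This applies where the CRF allows the entries of one event to be linked; if it does not, the SAP should say how such entries are counted.

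The cost is one or two SAP sentences and a programming condition, settled before unblinding. The first change uses an end date that is already collected. The AE form is not visible, so whether the second needs a linking field cannot be judged from the documents.

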6.1 Handling of Missing or Incomplete Dates for Adverse Events and Concomitant Medications

Adverse Events

Handling of partial dates is only considered for the start date. An adverse event with a partial start date is considered treatment emergent if:

- only the day is missing and the start month/year is the same or after the month/year of the first dose
- the day and month are missing and the start year is the same or greater than the year of the first dose date
- the start date is completely missing

Concomitant Medications

Handling of partial dates is only considered for the stop date. A medication with a partial stop date is considered concomitant if:

- only the day is missing and the stop month/year is the same or after the month/year of the first dose
- the day and month are missing and the stop year is the same or greater than the year of the first dose date
- the stop date is completely missing or the medication is ongoing

6.2 Summary of Assessments

The schedule of visits and procedures to be conducted at each visit are summarized in the Schedule of Study Procedures.

A 20x20 grid of black and white blocks. The grid contains several black L-shaped blocks, a central cross-shaped block, and various black bars of different lengths. The pattern is highly symmetrical and geometric.
